10.8 Drug STORAGE

Study drug will be stored in the clinical trials pharmacy at each site until it is dispensed. The standard temperature to store the study drug is at controlled room temperature, 15°C to 25°C. Furthermore, stability studies by OM Pharma on BV capsules at 30°C (for 5 years) and 40°C (for 6 months) have consequently shown the IMP can be used from 15°C to as high as 40°C without any impact to the

quality of the product. All temperature excursions beyond these temperatures must be reported to the BLIPA study team. OM Pharma will be informed by the trial manager.

Storage conditions, including the minimum and maximum temperatures will be monitored on a daily basis (Monday to Friday only) and according to temperature logging policy at the local site. Further details may be found in the study pharmacy manual.

Broncho-Vaxom granules (within capsules) dispensed to the parents or guardians for take-home dosing should remain in the blister packaging and stored as noted above until the point of use. Comprehensive instructions will be provided to the parent or guardian in order to ensure compliance with dosing and storage procedures.

10.9 Prescription and Dispensing of IMP(s), placebo(s)

A trial specific prescription form must be completed by the PI/delegated sub-investigator in order to prescribe the IMP. Study drug will be administered or dispensed only to parents or guardians of eligible children under the supervision of the PI/delegated sub-investigators.

10.10 Administration of IMP(s), placebo(s)

Both IMP and placebo will be supplied for the first twelve months during the baseline visit and provided once at the 12 months visit after this. Broncho-Vaxom granules are for oral use. They can be taken independently or mixed with a suitable age-related food (such as milk, yoghurt or puree). Supplementary study specific material including posters, presentations and a short video explaining IMP administration will be available to sites and participant parents/care givers. The IMP video will be available both at the baseline visit and as a link for remote access.

10.11 DESTRUCTION, RETURN, AND RECALL OF IMP(s) AND PLACEBO(s)

Used and unused IMP prescribed to children must be returned at the patient's face to face or clinic visit and recorded on the drug accountability log for trial monitoring. Study drug (expired or remaining at end of study) should be destroyed on site for safe disposal as per the site's local policy following written sponsor permission only. Delegated pharmacy personnel will document removal and destruction on drug accountability logs. OM Pharma will be informed by the trial manager that all residual IMP has been destroyed once full drug reconciliation is complete.

Should a recall need to be completed it should be conducted in accordance with the manufacturer's procedure and Pharmacy Manual.

10.12 DOSAGE SCHEDULES

Broncho-Vaxom 3.5mg granules will be the dose prescribed to all children and this will not change with age or size.

Study medication will be administered for 10 days of each month for the 24 month period. The dose can be taken at any time of day. The first treatment course in month one must be started within five weeks, plus or minus one week, of hospital discharge for the initial bronchiolitis episode. Subsequent treatment courses for the remaining 23 months should be started within the first 10 days of the month.

If a dose is missed or not taken on the scheduled day, patients will be instructed not to take double

or extra doses. In the case of a missed dose, the patient must take the missed dose on the following day and extend the number of days in that treatment course according to the treatment schedule. The treatment course needs to be extended by the number of days of missed doses within the same month. Forgotten capsules can be taken up to 10 days before the next dose or 10 days after the previous dose. Therefore, there always needs to be 10 days between 10-day treatment periods.

Should a child become unwell and vomits within one hour of taking the IMP, parents and guardians should notify the research team via text or email and extend the treatment course by one day. If vomiting occurs one hour or more after administration, full absorption of the compound can be assumed, and no further action is required.

10.13 Dosage modifications and delays

There is no modification to the study drug dosage due to age or otherwise.

If the child is unable to tolerate the trial medication or there are significant laboratory AEs deemed to be related to the drug, then the drug will be discontinued as per protocol. The child will remain in trial follow-up.

10.14 MANAGEMENT OF BRONCHO-VAXOM-SPECIFIC ADVERSE EVENTS

Hypersensitivity reactions should be reported to a medical professional (Primary care/A+E) and treated appropriately.

10.15 Known drug reactions and interventions with other therapies

Broncho-Vaxom drops contain methyl p-hydroxybenzoate (E 218) which may cause allergic reactions (possibly delayed).

No drug interactions are known up to now.

10.16 RECOMMENDED CONCURRENT TREATMENT

Not applicable.

10.17 Prohibited Medication

As there are no known drug interactions, there are no impacts on other medications being prescribed or taken.

10.18 STUDY RESTRICTIONS

There are no specific restrictions.

10.19 Management of overdose

Due to the nature of Broncho-Vaxom and the results of toxicity tests performed in animals, consequences of overdosage seems unlikely to happen. Overdose with Broncho-Vaxom did not reveal any safety concern. Lethal dose was determined to be higher than 2,000 mg/kg in mice and higher than 1,400 mg/kg in rats. Moreover, no signs of toxicity were observed after 2,000 mg/kg/day OM-85 PO administration for 6 months in rats or 100 mg/kg/day for 3 months in dogs.

10.20 ARRANGEMENTS FOR POST-STUDY ACCESS TO IMP AND CARE

As this is primarily an effectiveness study, study drug will not be available after the trial.

11 Equipment and Devices

No additional medical devices or equipment will be used in this study.

12 Pharmacovigilance

12.1 GENERAL DEFINITIONS

Term	Definition
Adverse Event (AE)	Any untoward medical occurrence in a participant to whom a medicinal product has been administered, including occurrences which are not necessarily caused by or related to that product. (See section 12.6 for AEs which do not require reporting).
Adverse Reaction (AR)	An untoward and unintended response in a participant to an investigational medicinal product which is related to any dose administered to that participant. The phrase "response to an investigational medicinal product" means that a causal relationship between a study medication and an AE is at least a reasonable possibility, i.e. the relationship cannot be ruled out. All cases judged by either the reporting medically qualified professional or the sponsor as having a reasonable suspected causal relationship to the study medication qualify as adverse reactions.
Serious Adverse Event (SAE)	A serious adverse event is any untoward medical occurrence that: Results in death. Is life-threatening. Requires inpatient hospitalisation or prolongation of existing hospitalisation. Results in persistent or significant disability/incapacity. Consists of a congenital anomaly or birth defect. Other 'important medical events' may also be considered serious if they jeopardise the participant or require an intervention to prevent one of the above consequences. NOTE: The term "life-threatening" in the definition of "serious" refers to an event in which the participant was at risk of death at the time of the event; it does not refer to an event which hypothetically might have caused death if it were more severe.
Serious Adverse Reaction (SAR)	An adverse event that is both serious and, in the opinion of the reporting Investigator or medical assessor, believed with reasonable probability to be due to one of the study treatments, based on the information provided.
Suspected Unexpected Serious Adverse Reaction (SUSAR)	A serious adverse reaction, the nature and severity of which is not consistent with the information about the medicinal product in question set out in the Reference Safety Information (RSI): In the case of a product with a marketing authorisation, in the summary of product characteristics (SmPC) for that product. In the case of any other investigational medicinal product, in the investigator's brochure (IB) relating to the study in question.

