1.3.4 Dosage, Regimen and route

The safety of BV has been assessed in trials in infants and young children. Bodemer et al gave 3.5 mg BV or placebo once a day continuously for 9 months to children 6 months to 7 years of age with 67% of the BV group < 3 years of age [15]. There were 5 adverse events possibly related to BV (cough and diarrhoea) and 2 related to placebo (diarrhoea). Sly et al, gave oral BV 3.5 mg or placebo once a day for 10 days per month to infants 3 to 9 months of age over 2 separate winter seasons, and concluded that BV was safe and tolerable with no difference in adverse events between the groups [14]. Using a different bacteria lysate (Pro-Symbioflor), Lau et al, gave newborns 10 drops of lysate 3 times a day continuously for 7 months [28]. There were 73 adverse events reported in the active and 74 events in the placebo groups, none considered to be related to the study medication. The ongoing ORBEX study (described above) has not found safety concerns with 3.5 mg BV given once a day for 10 days per month to infants 5 to 17 months of age.

This trial is categorised as:

Type B = Somewhat higher than the risk of standard medical care, (studies are those testing authorised medicinal products according to treatment regimens outside the marketing authorization).

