12.2 SITE INVESTIGATOR ASSESSMENT

The Principal Investigator is responsible for the care of the participant, or in their absence an authorised medic within the research team is responsible for assessment of any event for:

• **Seriousness**: Assessing whether the event is serious according to the definitions given in section 12.1.

- **Causality**: Assessing the causality of all serious adverse events/reactions in relation to the study treatment according to the definition given. If the SAE is assessed as having a reasonable causal relationship, then it is defined as a SAR.
- **Expectedness:** Assessing the expectedness of all SARs according to the definition given. If the SAR is unexpected (as per the RSI), then it is a SUSAR.
- **Severity:** Assessing the severity of the event according to the following terms and assessments. The intensity of an event should not be confused with the term "serious" which is a regulatory definition based on participant/event endpoint criteria.
 - o Mild: Some discomfort noted but without disruption of daily life
 - Moderate: Discomfort enough to affect/reduce normal activity
 - o Severe: Complete inability to perform daily activities and lead a normal life

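### Sections 12.1 and 12.2 use three unreconciled causality wordings, so a serious event that meets the adverse reaction test need not be classed as a SAR or assessed as a SUSAR

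*Protocol*

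**What the plan says.** The definitions table in Protocol section 12.1 sets the AR test as one where "a causal relationship between a study medication and an AE is at least a reasonable possibility, i.e. the relationship cannot be ruled out". The same row adds that cases judged by either the reporting professional or the sponsor as "having a reasonable suspected causal relationship to the study medication qualify as adverse reactions".

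The SAR row does not build on the AR row. It starts again from an adverse event that is serious and, in the opinion of the investigator or medical assessor, is "believed with reasonable probability to be due to one of the study treatments, based on the information provided". The SUSAR row then takes a serious adverse reaction as its starting point and adds inconsistency with the reference safety information.

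Section 12.2 gives the site investigator's task: "Assessing the causality of all serious adverse events/reactions in relation to the study treatment according to the definition given". It continues: "If the SAE is assessed as having a reasonable causal relationship, then it is defined as a SAR". Expectedness is assessed for SARs only: "If the SAR is unexpected (as per the RSI), then it is a SUSAR".

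**The concern.** A SAR would normally be an AR that is also serious, with one causality threshold for both. Here the table applies a possibility test to reactions in general and a probability test to serious ones.

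The SAR label opens the next steps. Only SARs are assessed for expectedness (12.2). Only a SUSAR leads the sponsor to break the blind for that child and report unblinded to the regulator and ethics committee (12.8.2). A threshold that depends on which row the assessor reads therefore bears on whether an expedited report is made, in infants treated for up to 24 months. SUSAR counts are also part of a secondary safety endpoint (2.5.2), and safety is to be summarised by relationship to the study drug (14.10). The trial has five or more UK sites, and a merger with Australian data is planned if conditions are met (1.3.7, 2.7), so several assessors will be applying these words.

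**Working it through.** No figure in the protocol depends on this wording, so there is nothing to recompute. The check is to set the passages side by side and follow one event through them.

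| Place | Step governed | Causality wording, in substance |
|---|---|---|
| 12.1, AR row | AE to AR | reasonable possibility; cannot be excluded |
| 12.1, SAR row | serious AE to SAR | reasonable probability |
| 12.2, causality item | SAE to SAR | reasonable causal relationship, judged by the definition given |
| 12.1 SUSAR row and 12.2 expectedness item | SAR to SUSAR | no new causality test; the event must already be a SAR |

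Take a serious event where the investigator cannot exclude the study drug but does not think it the probable cause.

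1. **AR row.** The test is met, so the event is an adverse reaction.
2. **SAR row.** The event is serious, but the probability test is not met. Read literally, it is not a SAR.
3. **Section 12.2.** The result depends on the reading. The rule's own words do not demand probability and are close to the second sentence of the AR row, which points to a SAR. The preceding sentence, however, sends the investigator back to the definition given, and for a serious reaction the obvious candidate is the SAR row. Nothing says which prevails.
4. **SUSAR.** If step 3 ends in no SAR, expectedness is not assessed and the event cannot be a SUSAR. If step 3 ends in a SAR, the normal route applies.

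The same opinion on the same event can therefore end in two classifications.

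The later steps limit the consequence as follows.

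- **Section 12.8:** SAEs go to the sponsor and the drug supplier within 24 hours whatever the causality opinion, apart from those the protocol exempts.
- **Section 12.8.1:** the chief investigator reviews every SAE within 72 hours, including relatedness and expectedness, and cannot lower the site's causality. The section gives no threshold. As the sponsor's medical assessor, the chief investigator is one of the people named in the SAR row, so the stricter wording is available to the second reviewer too. The bar on downgrading protects a positive site opinion. It does not by itself raise an event that the site left below the SAR line, although the chief investigator is free to do so.
- **Section 14.12:** the DMC is made aware of SAEs as well as SUSARs. The section spells the abbreviation out as severe; I read it as SAEs in the sense of 12.1.

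**The case against.** The strongest reply is that 12.2 is the working rule for sites and asks only for a reasonable causal relationship. The AR row admits all cases with a reasonable suspected relationship and makes no exception for serious ones. On a plain reading, an AR that is serious is a serious adverse reaction, which is where the SUSAR definition starts. Section 12.2 grades severity but not causality, so the protocol itself has no possible-but-not-probable category. This stands to the extent that a sensible assessor can reach the right result. It does not make the SAR row agree with the AR row, and 12.2 does not say that it overrides the table.

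A reader might infer three stronger things that the protocol does not support.

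- **That a possibly related serious event can never become a SAR or SUSAR.** Section 12.2 can be read to make it one, and the chief investigator can reach that view on second review.
- **That the earlier trial in section 1.3.4 shows this grade to be the important one for this product.** The five events described there as possibly related were cough and diarrhoea. They are not called serious, and the trial enrolled children from 6 months to 7 years. In this trial cough is exempt from reporting (12.6) and diarrhoea is listed as not unexpected (12.7). Those events do not illustrate a lost SUSAR.
- **That the safety comparison is biased between arms.** Site staff and the chief investigator are blinded (7.5), the chief investigator assesses SUSARs blinded (12.8.2), the AE and SAE counts do not depend on the SAR wording, and the safety analysis is descriptive (14.10). No route to differential bias is evident.

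**Conclusion.** The point holds as an inconsistency between adjacent safety definitions. Three causality wordings govern one chain of classification, and the SAR row, read literally, is stricter than the AR row. A serious event that meets the AR test need not be classed as a SAR, and so may miss expectedness assessment and SUSAR reporting.

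The exposure is to misclassification and a missed expedited report. It is not to serious events going unseen, because SAE notification, the second review and DMC awareness do not depend on the SAR label. The number of events affected cannot be derived: the protocol gives no expected rate of serious events and no distribution of causality opinions. Sample size, power and the efficacy analysis are untouched.

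The conclusion assumes that assessors may rely on the definitions table as written. The SAE form is not available to this review; if it already carries a single possibility test, the practical risk is smaller, but the protocol text still needs reconciling.

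**What to change.** Reconcile the passages to one causality wording.

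- In 12.1, define a SAR as an adverse reaction, as defined in the AR row, that meets any of the listed seriousness criteria.
- In 12.2, replace the causal-relationship phrase with the same reasonable-possibility wording, so that AR, SAR and SUSAR share one threshold.
- Check that the SAE form asks the causality question in those terms.

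The cost is two sentences in an amendment and a form check. The downside is possibly a few more SUSAR assessments and single-child unblindings by the sponsor. No analysis or sample size figure changes.

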12.2 SITE INVESTIGATOR ASSESSMENT

The Principal Investigator is responsible for the care of the participant, or in their absence an authorised medic within the research team is responsible for assessment of any event for:

• **Seriousness**: Assessing whether the event is serious according to the definitions given in section 12.1.

- **Causality**: Assessing the causality of all serious adverse events/reactions in relation to the study treatment according to the definition given. If the SAE is assessed as having a reasonable causal relationship, then it is defined as a SAR.
- **Expectedness:** Assessing the expectedness of all SARs according to the definition given. If the SAR is unexpected (as per the RSI), then it is a SUSAR.
- **Severity:** Assessing the severity of the event according to the following terms and assessments. The intensity of an event should not be confused with the term "serious" which is a regulatory definition based on participant/event endpoint criteria.
 - o Mild: Some discomfort noted but without disruption of daily life
 - Moderate: Discomfort enough to affect/reduce normal activity
 - o Severe: Complete inability to perform daily activities and lead a normal life

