12.4 Notification and recording of Adverse Events (AEs) or Reactions (ARs)

All AE and AR's are to be documented in the child's medical notes or other source data documents and the CRF by local site staff. AES will be collected monthly via the monthly questionnaire.

Once assessed, if the AE is not defined as SERIOUS, the AE is recorded in the participant's study file and the child is followed up by the research team.

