14.10 SAFETY ANALYSIS

Safety outcomes will be reported descriptively and will include the number and proportion of children experiencing an SAE or adverse event, summarised by treatment group and relationship to IMP.

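### The site causality assessment in 12.2 covers only serious events, while 14.10 reports all adverse events by relationship to IMP and 12.1 and 12.4 require adverse reactions of any seriousness to be recorded

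*Protocol*

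**What the plan says.** Protocol section 12.2 opens broadly: the PI or, failing that, "an authorised medic within the research team is responsible for assessment of any event for" four attributes. The bullets that follow differ in scope.

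- Seriousness is assessed for the event, whatever it is.
- Severity likewise: "Assessing the severity of the event according to the following terms and assessments".
- Causality is limited: "Assessing the causality of all serious adverse events/reactions in relation to the study treatment according to the definition given". The only outcome stated for this step is classification as a SAR.
- Expectedness is assessed for SARs.

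Section 12.4 requires both AEs and ARs to be documented in source and CRF. For the non-serious case it says that "if the AE is not defined as SERIOUS, the AE is recorded" in the study file and the child is followed up. It mentions no relatedness judgement.

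Section 14.10 then plans to report "number and proportion of children experiencing an SAE or adverse event, summarised by treatment group and relationship to IMP".

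**The concern.** Section 14.10 needs a relationship to IMP for every adverse event it tabulates, and it is not confined to SAEs. The section that tells the site what to assess asks for that judgement only when the event is serious. The output therefore depends on an input that the assessment rules do not require.

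The gap lies where most of the information on drug reactions is likely to be. Section 12.7 lists events that are not unexpected but must still be reported: diarrhoea, abdominal pain, nausea and vomiting, rash and urticaria. In most children these will not meet the criteria for a serious event. A review cited in section 1.3.2 found no reports of serious adverse reactions to bacterial lysates. Safety and tolerability is a secondary objective (section 2.3).

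An SAP cannot repair this. It can say how to tabulate relatedness, but the judgement itself is a blinded clinical one, made when the event is reported.

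**Working it through.** No arithmetic applies. The check sets the sections side by side and asks, for a non-serious reportable event, whether any section requires someone to judge its relatedness.

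| Section | Scope as written | Relatedness judgement for a non-serious AE? |
|---|---|---|
| 12.1, definition of AR | Any seriousness; causality judged by the reporting medic or the sponsor | Gives a criterion and a judge, but no instruction to assess each event |
| 12.2, lead-in | Any event | Implied at most |
| 12.2, causality bullet | Serious events | Not required |
| 12.2, severity bullet | The event, no limit | Not applicable; shows that the medic already grades each event |
| 12.4, recording | AEs and ARs, in source and CRF | Presupposed, since an AR differs from an AE only by causality |
| 12.4, non-serious path | Recorded and followed up | No step stated |
| 12.8.1, delegation | AEs, ARs, SAEs and SUSARs, to the CI | Covered in general terms |
| 12.8.1, review described | SAEs, within 72 hours, including relatedness | Not described |
| 14.10 | SAEs and adverse events, by arm and by relationship to IMP | Needed |

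1. Sections 14.10, 12.1 and 12.4 all rely on relatedness being known for non-serious events.
2. The one bullet that assigns the site judgement, the causality bullet in 12.2, stops at serious events.
3. The path for a non-serious event in 12.4 does not fill the gap.
4. Section 12.8.1 names the CI for AEs and ARs, but states no route by which non-serious events reach the CI for a relatedness judgement, and spells out that review only for SAEs.
5. AEs are collected through a monthly questionnaire that a parent may complete online (sections 7.8.4 and 12.4). A clinician's opinion on causality does not arise from that unless someone is told to give one.

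Scope: section 12.6 exempts cough, wheeze, lower respiratory tract illness and minor baby symptoms from reporting. The point therefore concerns reportable non-serious AEs, not every untoward event.

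**The case against.** The strongest reply is that the protocol, read as a whole, already provides for the judgement. Section 12.1 supplies a causality criterion with no seriousness limit and names who applies it. Section 12.4 requires ARs in the CRF, and an AR cannot be recorded without a view on causality. Section 12.8.1 puts medical assessment of AEs and ARs with the CI, and the absence of a deadline is not the absence of a duty. The 12.2 lead-in speaks of any event. The eCRF is not shown and may already carry a relatedness field. All of this stands. A reader might infer from 12.2 that non-serious reactions cannot be classified at all, or that the relationship column in 14.10 will be empty; the documents do not support that. What remains is that these sections point one way and the operative instruction to sites points the other.

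It could also be said that the words after the slash in the causality bullet bring in reactions of any seriousness. That reading is circular, because a reaction is by definition an event already judged related, and the bullet's only stated outcome is a SAR.

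Two further inferences should be resisted.

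- A reader might conclude that the rules for stopping treatment have no assessment behind them, because 10.13 refers to cases where "there are significant laboratory AEs deemed to be related to the drug" and section 8 to events resulting from treatment. Those decisions rest on the investigator's own judgement for the child, section 8 asks for a record at the next monthly contact, and sections 8, 8.1 and 10.13 contain routes that do not need relatedness.
- A reader might conclude that the comparison of possibly related events quoted in 1.3.4 from an earlier trial could not be repeated here because of 12.2. That does not follow: part of it is cough, which 12.6 exempts from reporting in any case, and the protocol does not say whether the events were serious.

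Finally, the safety endpoint in 2.5.2 is the number of AEs, SAEs and SUSARs. In a blinded 1:1 trial, an excess of diarrhoea or rash on active treatment would show in the counts by arm without any individual causality judgement. This limits the consequence, and rightly so.

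**Conclusion.** The inconsistency is real and should be corrected. Section 12.2 restricts site causality assessment to serious events, and 12.4 offers no step for the others, in conflict with 14.10 and with the definition and recording of ARs in 12.1 and 12.4. If sites follow 12.2 as written, relatedness of non-serious reportable AEs may be missing or inconsistent across sites. The 14.10 breakdown by relationship and any count of non-serious ARs would then be unreliable.

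The damage is confined to that descriptive breakdown. Between-arm AE counts are unaffected, and so is the classification of SARs and SUSARs, which 12.2 does cover. No number of events can be attached, since the protocol gives no expected AE rate and any figure would only multiply a guess. The conclusion assumes that most of the reactions listed in 12.7 will be non-serious and that no document outside the protocol, such as eCRF guidance, already instructs sites to judge every AE. If one does, the consequence largely falls away, but 12.2 would still contradict it.

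**What to change.** Reword the causality bullet in 12.2 along these lines: assess, while blinded, the causality of all reportable adverse events, serious and non-serious, apart from those exempted in 12.6. The natural assessor is the site medic who already grades seriousness and severity. Add one sentence to 12.4 that the relatedness judgement is recorded for non-serious events too. Check that the AE page of the eCRF has a relatedness field, and add one if it does not. Section 12.8.1 should say whether the CI reviews relatedness of non-serious AEs or only of SAEs.

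The cost is two or three sentences, at most one eCRF field, and a brief extra judgement per AE by someone who is already assessing that event. It is best done while events are still being reported, because judgements made long afterwards are less complete and less consistent.
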